8.8 Emergency Unblinding

It is extremely unlikely that a site researcher other than the administrator/practitioner responsible for setting participants up on the intervention would need to be unblinded, even in cases of risk. The trial code would only need to be broken for valid medical or safety reasons, for example in the case of a serious adverse event, where it is necessary for the investigator to know whether there is a relationship between condition and adverse events. In these circumstances, the research team will remain blinded. Where a person raises clinical relevant concerns or reports risk, and where knowing the trial condition is relevant, one of the project team dealing with this participant can potentially be unblinded to the participant's condition to support their care and further support them — in many cases, it may not be necessary to know the condition. The action taken according to the risk protocol would be the same, regardless of condition. The PI will be able to request the condition from the CTU if there are any adverse events. In the case of a serious adverse event, it will be necessary for principal investigator / site-relevant practitioner to be unblinded for safety reasons.

8.9 Baseline data

Baseline data will be collected after the screening section of the screening website.

8.10 Trial assessments

Assessment will take place at baseline (start of treatment) and then at 6 weeks post baseline (equating to end of treatment) and 12-weeks post baseline. The 3-month follow up will be the primary endpoint. All assessments will be through EXCTU managed EDC system. Only if participants have not responded to email and text prompts to complete their follow ups at 6 and 12 weeks will they be contacted by phone and asked to provide the primary outcome measures only on the telephone. The results of the assessments are only to collect research data for the trial and will not be provided to medical practitioners. The only exception to that would be if a participant indicates suicide risk and asks us to provide their assessment results to their medical practitioner. They would need to give written consent for this and provide us with the contact details to do so. See risk protocol in Appendix.

At the end of treatment, participants that have received the sbLICBT resiliency intervention will receive an email asking them to participate in an acceptability focus group and Section 12 of the protocol provides further information on this.

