6.1 Patient registration/randomisation procedure

At the point of randomisation participants will be automatically registered on to the trial using the electronic data capture (EDC) system. Randomisation is after the online consent, the screening process and after the online baseline assessment. There is a two-part consent process which in the first part asks for permission to screen and take part in the assessment. The second part of consent with agreement sought to take part in the study is taken prior to baseline assessment. Participants can stop the assessment at any stage and be emailed a link to return the screening website. this allows them to have time to consider the participant information which they have read on screen and which is emailed to them. The email link will be live for 14 days. After this time the participant will need to contact the site to ask for the link to be reset.

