8.3 Consent

We anticipate that university students will be autonomous independent young adults who are legally recognised as being at or above the age of majority and able to provide their own informed consent to their participation in research (aged 16 or over for the UK).

Young people will be initially routed to or seek out the study website and will be provided with the participant information sheet, consent form A and data protection policy to review on the trial electronic platform, prior to completing screening measures. There will be a check box at the bottom of the information sheet which participants will need to check before they can sign the consent form. Participants will then be asked to read, date, and electronically sign consent form A and provide their contact details. Consent form A asks for consent to undertake the assessment and confirmation that the participation understands the nature of the study.

When consent is given, they will be assigned a screening ID number and automatically be emailed a copy of the consent form, information sheet and data protection /privacy policy or given the option to download these documents. The recruit will then be asked to complete brief background screening measures to determine eligibility on the online screening website. Non-excluded recruits can stop and save their assessment at any time and be emailed a link to return to the assessment. The participant will have 2 weeks in which to be able to return to their part completed assessment. After this time, they would need to start the assessment again if they wanted to take part.

If a participant completes the screening assessment and is eligible for the trial, then they will be presented with consent form B1 which asks them to consent to taking part in the trial. Recruits are advised that they can take time to consider taking part and can save their assessment whilst they do so.

On completion of consent form B1 participants are then asked to complete the full baseline assessment measures. Once this has been completed, the recruit is randomised and will be given a unique study participant trial number, and they are informed that they have completed the baseline assessment and that they will be contacted to be informed of the outcome of the randomisation.

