8.6 Method of implementing the randomisation/allocation sequence

Participants will be randomised by a web service which interfaces with the EXCTU EDC system and database. This will be an automated process. The EXCTU database will send an unblinded team member (administrator/therapist) indicating when an individual [by study ID] has been randomized to the active intervention. This team member will then access the relevant details in the EXCTU database and manually set up the participant in the internet platform using administrator rights via the internet platform dashboard. A system automated email will be sent to the participant indicating the condition to which they are randomised, informing them what to expect, date of sbCBT group to next intervention arm and asking the participant to confirm receipt by return of email to unblinded team member. The team member will send up to 6 reminder emails to any participant that has failed to confirm receipt.

Failure to receive confirmatory email: the relevant unblinded team member will also be able to monitor if the participant has accessed the intervention and check if there are any difficulties and encourage to sign-up.

Detailed procedure for randomisation:

- 1. Participants are block randomised (30 participants per arm) into the 2 arms (DTC control versus sbLICBT) on an intention-to-treat basis.
- 2. Block randomisation will continue until 120 participants (6 iterations of 60 participants) are randomised.
- 3. The system must record the allocation and the date randomised.
- 4. The trial manager and at least one other researcher remain blind to the allocation; the participant will be aware of which intervention received. The practitioner / administrator will be unblinded in order to set-up participant on internet platform.
- 5. On successful randomisation, a finish page is displayed with a message telling the participant to look for an email message from the trial team.

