9 INTERVENTIONS

9.1 Written Strength-Based Low-Intensity CBT (SBLICBT) Resiliency Intervention with Support on Demand

The intervention is reported according to the Template for Intervention Description and Replication (TIDieR) Checklist (Hoffman et al., 2014).

Table 8 TIDieR Checklist

Item	Description
Brief Name	Bounce Back: Finding Your Inner Strength
Why	As a consequence of being exposed to increasing demands presented by University life, students now have an increased likelihood of experiencing mental health difficulties resulting in long-term disadvantage. Enhancing resiliency to enable students to cope when facing such demands has potential to prevent the development of mental health difficulties. A protocol for a strength-based CBT intervention (Padesky & Mooney, 2012) has informed the development of a written low-intensity CBT intervention. To enhance resiliency, the participant engages with the written intervention to work through four-steps –(1)Record a successful regular activity, (2)Build a personal model of resiliency, (3)Apply personal model of resiliency to an area found challenging, (4)Practice resilience.
What	Written strength-based low-intensity CBT intervention with an initial 60-minute didactic group session to provide an overview of the resiliency intervention and introduce availability of 'on demand' support. On-demand support will be available face to face, virtual, phone or by email for up to 6 weeks.
Who Provided	A Psychological Wellbeing Practitioner (PWP) trained to support the intervention with supervision provided.
How	Following a 60-minute didactic group session where the intervention introduced, participants will be encouraged to engage with the written CBT self-help intervention over the following 6 weeks. 'On demand' minimum contact 'Plan-Do-Review' support will be available on request, over face to face or by email.
Where	University of Exeter.

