10 OUTCOME MEASURES/ENDPOINTS

10.1 Feasibility outcomes (Appendix 1)

Table 9 Feasibility Outcomes

	asibility Outcomes	T		
	people accessed study web site			
Number of	people complete screening			
questions				
Number of	people screened out	If Yes - Reason	Repor	t by demographics
Number of	people consented		Repor	t by demographics
Number of	people randomised		Repor	t by demographics
	ndomisation maintained	Yes		No
Study arms				1
sbLICBT	Number attended group session	Report by demo	graphic	ς
3521051	Number completed baseline	Data completion of each item for each outcome		
	outcome measure	measure	. Or cac	Tricent for each outcome
	Difference in WSAS score	Overall and score per item		
	screening v attended group session	Overall and scor	e per itt	CIII
	Number completed end of	Data completion	of oacl	h item for each outcome
	treatment outcome measures (6	measure	i Oi eaci	ir item for each outcome
	•	illeasure		
	weeks post baseline)	Data completies	of and	h itam far asah sutasas
	Number completed final outcome	-	i or eaci	h item for each outcome
	measures 12-week post baseline	measure	1	
	Number of participants requesting	Report by demo	grapnic	S
	support			
	Number of support episodes			
	requested			1
	Number of each type of support	Face to Face		e-mail
	episode requested			
DTC	Number completed baseline			
	outcome measure			
	Difference in WSAS score	Overall and scor	e per ite	em
	screening v baseline			
	Number completed outcome			
	measures at 6 weeks post baseline			
	Number completed final outcome			
	measures 12-week post baseline			
DTC move	Number attended group session	Report by demo	graphic	S
to				
sbLICBT				
	Number completed baseline	Data completion	of	Number completed
	outcome measure	each item for ea	ch	baseline outcome
		outcome measu	re	measure
	Number completed end of	Data completion	of	Number completed
	treatment outcome measures	each item for ea		end of treatment
		outcome measu	re	outcome measures
	Number completed final outcome	Data completion	of	Number completed
	measures 12-week post baseline	each item for ea		final outcome
		outcome measu		measures 12-week
			-	post baseline
	Number of participants requesting	Report by demo	graphic	•
	support		0. ~Pc	-
		l		

Number of support episodes requested		
Number of each type of support episode requested	Face to Face	e-mail

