10.3 Timeframe for Administration of Demographic and Outcome Measures

Table 11 Outcome measures timeframe

	Time Period		_	
Outcome Measure	Screening	Baseline (Treatment Start)	6 Weeks Post Baseline (Treatment End)	12 Week Post Baseline
Demographic	x			
Brief Resiliency Scale		X	x	х
PHQ9	x	x	x	x
GAD7	X	X	x	x
WSAS	X	X	x	x
Feasibility Outcomes				x

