12.6.2 Repeated measures comparison including all timepoints

Secondary outcomes (resilience, anxiety, depression, work and social adjustment) will be taken at baseline, 6 weeks (treatment duration) and 12 weeks post randomisation. Secondary continuous outcomes will be reported descriptively (mean and standard deviation (SD)) and inferential comparisons will be reported between the two conditions (1) *sbLICBT*; (2) *DTC* to explore potential effect sizes and confidence intervals.

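### Six weeks after baseline is labelled end of treatment, but the six-week treatment runs from a later group session and nothing limits the gap

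*Protocol*

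**What the plan says.** Section 8.10 equates the assessment times with the treatment period: "Assessment will take place at baseline (start of treatment) and then at 6 weeks post baseline (equating to end of treatment". The timetable of measures in section 10.3 repeats the label, "Baseline (Treatment Start", and marks the 6-week column as treatment end. Section 12.6.2 takes the outcomes at "6 weeks (treatment duration) and 12 weeks post randomisation".

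The procedures give a different order.

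- Section 6.1: "Randomisation is after the online consent, the screening process and after the online baseline assessment".
- Section 8.3, on the baseline measures: "Once this has been completed, the recruit is randomised and will be given a unique study participant trial number".
- Section 8.6: "Participants are block randomised (30 participants per arm) into the 2 arms". Randomisation is automated and the participant sees a finish page. An email then gives the allocation and the date of the group.
- Section 9.1: after a 60-minute group session, "participants will be encouraged to engage with the written CBT self-help intervention over the following 6 weeks".

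Two further places do not fit either account. The procedures schedule in section 8.11 marks access to the intervention as available at baseline. The feasibility table in section 10.1 compares WSAS "screening v attended group session" in the sbLICBT arm, but screening against baseline in the delayed treatment control (DTC) arm.

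**The concern.** If baseline comes before randomisation and the six weeks of treatment begin at a later scheduled session, a questionnaire sent six weeks after baseline does not measure the end of treatment for anyone who waited. Four parts of the protocol depend on that date:

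- Engagement (section 8.14) is asked at 6 weeks post baseline, possibly before the participant has had six weeks, or any time, to engage.
- The focus-group email (section 11.1) goes out at the same point and tells recipients that the support period is over.
- The number completing end-of-treatment measures (section 10.1) is a feasibility outcome, and feasibility is the primary analysis (section 12.5). The count would describe a different moment from its label.
- The DTC arm is treated once the intervention arm has finished its six weeks (section 9.2). The position of week 12, the primary endpoint in section 10.4, relative to that crossover depends on the wait.

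These times are built into the electronic data capture (EDC) triggers. A later analysis plan cannot recover a questionnaire that was sent at the wrong time.

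**Working it through.** **The plan's own identity.** Let w be the weeks from baseline to the group session.

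- End of treatment = baseline + w + 6 (sections 8.3, 8.6 and 9.1).
- Stated end of treatment = baseline + 6 (sections 8.10 and 10.3).
- The two agree only if w = 0. The protocol gives no value and no upper limit for w.

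**Week 12.** The earliest DTC start is baseline + w + 6, so week 12 falls 12 − (w + 6) = 6 − w weeks after it. With w = 0, week 12 comes six weeks after the earliest crossover. With w = 6 it coincides with it, and with w above 6 it comes before it.

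**Illustration of size.** Inputs from the protocol are 60 participants per cohort (30 per arm, sections 8.6 and 12.2), six weeks of treatment, and two cohorts over 28 weeks (section 12.2). The following is an assumption and is not in the protocol: a cohort completes baseline evenly over W weeks and one session is held when it is full, so w is uniform on 0 to W. Then:

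- mean weeks of treatment at week 6 = 6 − W/2 if W ≤ 6, and 18/W if W > 6;
- share assessed at week 6 before the session = max(0, 1 − 6/W);
- share whose six weeks are complete by week 12 = min(1, 6/W).

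| W (weeks) | Mean exposure at week 6 | Not yet treated at week 6 | Six weeks complete by week 12 |
|---|---|---|---|
| 3 | 6 − 1.5 = 4.5 | 0% | 100% |
| 4 | 6 − 2 = 4.0 | 0% | 100% |
| 8 | 18/8 = 2.25 | 1 − 6/8 = 25% | 75% |
| 14 | 18/14 = 1.3 | 1 − 6/14 = 57% | 43% |

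W = 14 is 28/2, the slowest pace consistent with section 12.2. W = 8 is an intermediate case: (28 − 12)/2, if 12 weeks of follow-up have to fit inside the 28. W = 3 and W = 4 stand for fast accrual.

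**The case against.** The strongest reply is that baseline was meant to coincide with the session. In the section 10.1 table, the sbLICBT rows list group attendance before the baseline measure, and section 10.3 has no separate assessment at the session, so the WSAS row may simply mean baseline. The section 8.11 schedule also gives access at baseline, and section 8.6 has staff set up the participant on the platform after randomisation. On that reading the label in section 8.10 is correct. However, it contradicts sections 6.1 and 8.3, and it would place baseline after randomisation in the sbLICBT arm. It therefore adds to the conflict.

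A second reply concerns size, and it stands. No section says that a session waits for 60 recruits or how fast a cohort fills. The 14-week case is an extreme: 28 weeks of recruitment from 1 June 2023 would end on about 14 December, and 12 weeks of follow-up would run to about 7 March 2024, past the revised project end of February 2024 in section 8.13. Table 7 defines the 28 weeks differently, from first group session to final follow-up. A reader might infer that many or most participants will be assessed before treatment, but the protocol does not establish that.

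Third, timing follow-up from baseline in both arms keeps the randomised comparison balanced, and the main aim is feasibility. That also stands. The wait changes how much treatment the comparison reflects; it does not by itself favour an arm. A reader might likewise infer from the WSAS rows that the arms have different time zeros. Those rows are consistent with that but do not show it.

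**Conclusion.** The point holds as an internal contradiction with practical consequences. Sections 8.10 and 10.3 treat baseline as the start of treatment, while sections 6.1, 8.3, 8.6 and 9.1 put an unlimited wait between the two. Week 6 is mislabelled for everyone whose wait is not zero, and that conclusion needs no assumption.

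The size does need one and cannot be settled from the protocol. Under even accrual with a session when the cohort is full, it ranges from a mean shortfall of 1.5 weeks or less (cohort filled in 3 weeks or less) to a mean exposure of 1.3 of 6 weeks with 57% untreated (14 weeks). The upper figure is a bound under that pattern and should not be read as a forecast. The sponsor should resolve this before the EDC triggers are fixed.

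**What to change.** - Reconcile sections 6.1, 8.3, 8.6, 8.10, 8.11, 9.1, 10.1, 10.3 and 12.6.2 on when baseline is taken, when treatment starts, and from which date follow-up is counted.
- Send the 6- and 12-week questionnaires in both arms of a cohort from one date, that cohort's sbLICBT group session. Tie the engagement questions and the focus-group email to the same date.
- Keep baseline before randomisation, and open each cohort's baseline and randomisation step only within a short, stated window before its session. Individual automated randomisation can stay; randomising whole cohorts in a batch is not required.
- Use the same reference point for both arms in the WSAS rows of the section 10.1 table.
- Record the lag from baseline to session for each participant and report it.

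The cost is a change of trigger date in the EDC, a gate on when baseline opens, and protocol wording. Some recruits would wait between screening and baseline, and a few may drop out before randomisation. The 14-day limit on the saved-assessment link (sections 6.1 and 8.3) would need adjusting. Re-anchoring puts week 12 at the same distance from the earliest DTC start for everyone, but it does not move week 12 ahead of that crossover.
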